12.8.2 Sample Size Determination

The following power calculations were computed using the IGA efficacy results from the Pimecrolimus Lotion, 1% (Elidel) NDA 21-302. Considerations were given the change in expected entry level severity of the current study. Nquery Advisor Version 7.0 with the Fisher's exact test option was used to calculate the power using a 2-sided test with an alpha of 0.05. The following table presents the efficacy estimates used in this power calculation.

Percent Dichotomized IGA Success* for Treatment Groups

	Pimecrolimus Lotion, 1%	Vehicle
Percent	23.6%	6.3%
Success		

* Success was defined as at least a 2-grade improvement from Baseline in the IGA score and an IGA score equating to "Clear" or "Almost Clear".

Overall, 232 IDP-124 Lotion treated subjects and 116 vehicle lotion treated subjects will have greater than 95% power to detect a statistically significant outcome for a 2-sided test with an alpha level of 0.05.

It was noted that the estimates extracted from the above studies are based on the LOCF method of handling missing values while the proposed Phase 3 analysis will account for missing values using multiple imputations. The power stated above sufficiently exceeds 95% which will compensate for the difference in handling of missing data.

12.8.3 Handling of Missing Data

The primary method of handling missing efficacy data will be MCMC multiple imputation. This method does not rely on the assumption of data missing at random. Additionally, imputation will be conducted within each treatment group independently, so the pattern of missing observations in 1 treatment group cannot influence missing value estimations in another.

For each efficacy variable (IGA, EASI, pruritus severity), the following steps will be performed to impute missing data:

1. For each treatment group, create a data set containing subjects with observed values and those needing estimation by MCMC. The missing efficacy data in each data set will be filled in using the MCMC method 5 times to generate 5 data sets. The resulting data set for each treatment group will be combined into 1 complete data set for each imputation.

2. Syntax:

```
proc mi data=datain out=dataout seed=&seed. nimpute=5 <options>; where trtpn=(1 or 2); mcmc chain=multiple; var baseline week1 week2 week4 week6 week10; run;
```

- 3. Imputed data will be used to determine dichotomized success/failure values, as appropriate.
- 4. Each complete data set will be analyzed with the appropriate test (CMH, Analysis of Covariance).
- 5. CMH statistics will be normalized using the Wilson-Hilferty transformation.
- 6. The results from these analyses will be combined into a single inference using SAS PROC MIANALYZE.

A total of 6 random seeds will be needed for the multiple imputation process for the primary and secondary variables. The 6 random seeds have been prespecified by using a random number generator:

- Seed for IGA endpoints for IDP-124 = 144527508
- Seed for IGA endpoints for Vehicle = 622040939
- Seed for EASI endpoints for IDP-124 = 1706910659
- Seed for EASI endpoints for Vehicle = 2030081039
- Seed for pruritus severity endpoints for IDP-124 = 1758840189
- Seed for pruritus severity endpoints for Vehicle = 566468919

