11.2.3 Eczema Area Severity Index (EASI)

At Day 1 (Baseline), and Weeks 1, 2, 4, 6, and 10, the EASI will be calculated. The EASI is defined as a composite score based on the evaluated severity of 4 key signs of AD (i.e., erythema, infiltration/papulation, excoriation and lichenification), and the extent of disease in each of the 4 body regions (i.e., head/neck, trunk, upper limbs, and lower limbs).

The area of involvement (affected by inflammation, not including dry skin) of each of the 4 body regions will be determined and represented by a numeric coded value based on a scale from 0 to 6 as described below (the investigator is required to record the affected TBSA on the eCRF).

Score	Area of Involvement
0	No eruption
1	< 10%
2	10%-29%
3	30%-49%
4	50%-69%
5	70%-89%
6	90%-100%

The 4 body regions are assessed separately for each sign/symptom, and the average degree of severity of each sign in each of the 4 body parts is assigned a score of 0 (none) to 3 (severe) on a scale that allows half-unit increments.

Signs and Symptoms of Atopic Dermatitis

Score	Grade	Description		
Eryther	Erythema			
0	None	No erythema present		
1	Mild	Mild erythema, very light pink		
2	Moderate	Pink red clearly distinguishable perceptible erythema		
3	Severe	Bright red		
Infiltra	tion/Papulatio	n		
0	None	None		
1	Mild	Barely perceptible elevation		
2	Moderate	Clearly perceptible but not extensive		
3	Severe	Marked and extensive elevation		
Excori	ation			
0	None	None		
1	Mild	Scant evidence of excoriations with no signs of deeper skin damage (erosion, crust)		
2	Moderate	Severe linear marks of skin with some showing evidence of deeper skin injury (erosion, crust)		
3	Severe	Many erosive or crusty lesions		
Lichen	Lichenification			
0	None	None		
1	Mild	Slight thickening of the skin discernible only by touch and with skin markings minimally exaggerated		
2	Moderate	Definite thickening of the skin with skin marking exaggerated so that they form a visible crisscross pattern		
3	Severe	Thickened indurated skin with skin markings visibly portraying an exaggerated crisscross pattern		

The EASI score (range from 0 to 72) will then be calculated using the following formula:

Body Region	EASI Score	
Head/neck	(E+I+EX+L) x Area x P*	
Upper limbs	(E+I+EX+L) x Area x P*	
Trunk	(E+I+EX+L) x Area x P*	
Lower limbs	(E+I+EX+L) x Area x P*	
Total body score =	Sum of each region score	

E = erythema; I = infiltration/papulation; EX = excoriation; L = lichenification

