12.5.2 Secondary Efficacy

The secondary efficacy endpoints will be:

- Dichotomized IGA score at Week 4 where treatment success is defined as achieving clear to almost clear (i.e., a score of 0 or 1) and at least a 2-grade improvement in the IGA. These data will be analyzed using the CMH test stratified by analysis center.
- The percentage of subjects with EASI 75 (at least a 75% reduction) at Week 6 where the EASI score is defined as a composite score based on the evaluated severity of 4 key signs of AD (i.e., erythema, infiltration/papulation, excoriation, and lichenification), and the extent of disease in each of the 4 body regions (i.e., head/neck, trunk, upper limbs, and lower limbs) will be analyzed using the CMH test stratified by analysis center.
- The percentage of subjects with EASI 75 (at least 75% reduction) at Week 4 will be analyzed using the CMH test stratified by analysis center.
- Dichotomized IGA score at Week 10 where treatment success is defined as achieving clear to almost clear (i.e., score of 0 or 1) and at least a 2-grade improvement in the IGA from Baseline. These data will be analyzed using the CMH test stratified by analysis center.
- The percentage of subjects with EASI 75 (at least 75% reduction) at Week 10 will be analyzed using the CMH test stratified by analysis center.
- Percentage of subjects with score of "None" or "Mild" and at least a one-grade improvement from Baseline in the severity of pruritus at Week 2
- Percentage of subjects with score of "None" or "Mild" and at least a one-grade improvement from Baseline in the severity of pruritus at Week 1Dichotomized IGA score at Week 2 where treatment success is defined as achieving clear to almost clear (i.e., score of 0 or 1) and at least a 2-grade improvement in the IGA from Baseline. These data will be analyzed using the CMH test stratified by analysis center.

Evaluation of the secondary efficacy variables will use a gated sequential procedure starting with the comparisons of the first bulleted item and proceeding onto the next item. The process will terminate if a nonstatistically significant value is observed.

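### EASI is imputed from a normal model on the raw score with no stated bound or transformation, so negative draws would count as EASI-75 responses and, under plausible skew, modestly dilute the treatment difference

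*Combined protocol and SAP*

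**What the plan says.** Section 12.8.3 of the protocol states: "The primary method of handling missing efficacy data will be MCMC multiple imputation". It then applies one recipe to three variables: "For each efficacy variable (IGA, EASI, pruritus severity), the following steps will be performed to impute missing data". The code is "proc mi data=datain out=dataout seed=&seed. nimpute=5 <options>", followed by "mcmc chain=multiple; var baseline week1 week2 week4 week6 week10; run". The arms are handled separately ("imputation will be conducted within each treatment group independently"), and responder status is derived last: "Imputed data will be used to determine dichotomized success/failure values, as appropriate".

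Section 11.2.3 fixes the scale: "The EASI score (range from 0 to 72) will then be calculated using the following formula". Section 12.5.2 makes EASI-75 a secondary endpoint at Weeks 6, 4 and 10, for example "The percentage of subjects with EASI 75 (at least 75% reduction) at Week 4 will be analyzed using the CMH test". These are the second, third and fifth tests in a fixed sequence that stops at the first non-significant result.

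Section 12.8.3 states no transformation, minimum, maximum or rounding for EASI.

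**The concern.** The MCMC statement in PROC MI draws missing values from a multivariate normal distribution. EASI has a floor at 0, and the responder cut lies close to that floor. By the Section 11.2.3 formula, a subject aged 8 or older with all four signs at 2 and less than 10% involvement in every region scores 8 × 1 × (0.1 + 0.2 + 0.3 + 0.4) = 8. The EASI-75 cut is then 0.25 × 8 = 2. Entry requires at least 5% affected surface area and IGA 3 or 4, with no upper limit on extent, so a long right tail is plausible. A symmetric distribution fitted to such data puts mass below zero, and usually too much mass below the cut when few subjects truly respond.

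If the excess is larger on vehicle than on active, the treatment difference shrinks. An EASI-75 test could then miss significance and end the sequence. The detailed sensitivity analyses in Section 12.5.5 (LOCF, repeated measures, tipping point) concern IGA success at Week 6 and would not reveal this.

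**Working it through.** **The plan's own figure.** The only stated power is for IGA success: 23.6% vs 6.3%, 232 vs 116, Fisher's exact test, two-sided 0.05, greater than 95% (Section 12.8.2). Exact enumeration gives 99.3%, so the statement reproduces. It does not involve EASI.

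**Why a negative draw is a response.** With baseline B and imputed score Y, EASI-75 requires (B − Y)/B ≥ 0.75, that is Y ≤ 0.25B. Every Y < 0 satisfies this. So does Y = 0, so setting negative values to 0 changes no classification.

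**Size of the bias.** In one arm, with responder status known for everyone else:

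bias = fraction missing × (imputed response rate among the missing − true response rate among the missing).

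The documents give no EASI mean, SD, skewness, EASI-75 rate or dropout rate, so all inputs to the simulation are assumptions:
- log-normal EASI capped at 72, baseline CV 0.6 to 0.9;
- true Week 6 EASI-75 of about 7% or 13% on vehicle and 24% or 36% on active;
- monotone dropout giving 5% to 20% missing at Week 6, unrelated to response or higher in those doing worse;
- 5 imputations per arm from a Bayesian normal model on the raw visit scores, with Week 10 left out of the simulated model;
- 150 trials per scenario.

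Examples with 20% missing, dropout unrelated to response and baseline CV 0.9:

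| Arm (true overall rate) | True rate in missing | Imputed rate | Negative draws | 0.20 × (imputed − true) | Simulated bias |
|---|---|---|---|---|---|
| Vehicle (12.8%) | 14.1% | 23.9% | 15.9% | +1.96 | +2.0 |
| Active (24.3%) | 24.7% | 29.9% | 17.9% | +1.04 | +1.0 |
| Active (36.3%) | 36.4% | 35.2% | 20.3% | −0.24 | −0.3 |

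Negative draws alone do not create bias: the third row has the most of them and almost no bias. What matters is whether the normal tail below 0.25B is larger than the true one, and that depends on the true response rate and the skew.

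Over all scenarios:
- Vehicle: 6% to 17% of imputed values are negative, and 10% to 25% count as EASI-75 against 2% to 15% truly responding. The rate rises by 0.4 to 0.8 points at 5% missing, 0.8 to 1.4 at 10% and 1.6 to 2.6 at 20%.
- Active: +0.2 to +1.6 points at a true rate of 24%, and −0.3 to +0.8 at 36%.
- Difference: a change of about 0 (1.6 − 1.6) to about 3 points (2.6 + 0.3 = 2.9), mostly a shrinkage.

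**Alternatives in the same simulation.** Log-scale imputation has bias −0.1 to +0.1, but the data are log-normal, which favours it. Redrawing within 0 to 72 gives −0.6 to +0.6 on vehicle but 0.0 to −3.4 on active. At a true 36.0% with 20% missing, the rate among the missing falls from 36.4% to 19.9%, and 0.20 × (19.9 − 36.4) = −3.3, against −3.4 simulated.

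A second simulation used 10% to 20% missing, log-normal and non-log-normal EASI, with and without values set to zero. The raw normal model gave +0.5 to +2.1 points on vehicle and +0.1 to +0.8 on active. Log(EASI + 0.5) and predictive mean matching both stayed within about 0.5 points in both arms.

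**Effect on power.** Two-proportion normal approximation (pooled variance under the null), 232 vs 116, two-sided 0.05, active rate held fixed, imputation variance and stratification ignored:

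| Assumed true rates | Vehicle shift | Power |
|---|---|---|
| 40% vs 18% | +1.4 to +1.8 | 99.2% to 98.1%–97.6% |
| 24% vs 7% | +2.6 | 98.9% to 92.4% |
| 24% vs 13% | +1.4 | 69% to 55% |

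Holding the active rate fixed overstates the loss wherever active also moves up, as it did at a true 24%.

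**The case against.** The strongest reply is that the model is not shown to be unbounded. `<options>` sits in the PROC MI statement, where MINIMUM=, MAXIMUM= and ROUND= are set, and Sections 12 and 12.8 promise a separate SAP. This stands in part: the plan leaves the bounds open, and it would be wrong to say that the final program has none. It does not settle the matter. TRANSFORM is a separate statement that the placeholder cannot hold, and bounding alone can pull the active rate down.

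A reader might infer that the vehicle rate is inflated as a matter of fact and that the gated sequence will stop early. The documents do not support that. They give no EASI distribution, response rate or amount of missing data. The bias follows the true response rate and the skew, not the vehicle label, and the active arm can rise as well. With a large effect such as 40% vs 18%, the power lost is only 1.1 to 1.6 percentage points. The shift of 1.4 to 1.8 points is about half of one standard error of the vehicle rate, √(0.18 × 0.82/116) = 3.6 points.

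It is also fair that log imputation looks best on log-normal data. The second simulation, which included other shapes, answers most of this.

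**Conclusion.** The point holds as a gap in specification with a probable, modest cost. Section 12.8.3 applies a normal model to raw EASI, states no transformation or bound, and dichotomizes afterwards, so any negative draw would be an EASI-75 response. Under the assumed right skew, the likely result is dilution of the difference by about 0 to 3 points in a Week 6 comparison. The same model feeds Weeks 4 and 10, which were not simulated. The power cost is small if the EASI effect is large and material only if it is modest. The likely direction is against the active arm, so this is not a probable source of a false positive. The primary IGA comparison and its stated power do not depend on it.

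The sizes rest on assumed skew, response rates and 5% to 20% missing data. With little missing data, or less skew, the bias would be smaller.

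**What to change.** Before unblinding, add an EASI-specific rule to Section 12.8.3 and the SAP, choosing one of:

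1. **Log scale.** Impute log(EASI + c) at baseline and all weeks with a TRANSFORM statement, keeping the MCMC method, the separate arms and the EASI seeds. Back-transform, then derive EASI-75. Fix c in advance; 0.5 is the value that was tested.
2. **Predictive mean matching** (FCS REGPMM), then derive EASI-75.

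In either case, write out the contents of `<options>`. Do not rely on capping at 0, which changes no EASI-75 classification, or on MINIMUM=0 alone, which can bias the active arm downward.

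Option 1 costs one extra statement and one SAP sentence. Option 2 also replaces the named MCMC method for EASI, so the description of the primary missing-data method would need an exception.

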11.3.5 Pregnancy

All pre-menses females (9 and older) and female subjects of childbearing potential must use an effective method of birth control during the course of the study, in a manner such that risk of contraceptive failure is minimized. Abstinence is allowed as a birth control method.

Before enrolling a female subject of childbearing potential in this clinical study, the investigator must review the following information about study participation:

- Informed consent/assent requirements.
- Contraceptives in current use.

Following review of this information and appropriate counseling for the subject and their parent/legal guardian, the investigator or designee and the subject and parent/legal guardian must sign the assent/informed consent before study enrollment.

During the study, all pre-menses females (9 and older) and female subjects of childbearing potential should be instructed to contact the investigator immediately if they suspect they might be pregnant (e.g., missed or late menstrual period).

If a subject or investigator suspects that the subject may be pregnant prior to study enrollment, the study drug must be withheld until the results of laboratory pregnancy testing are available. If pregnancy is confirmed, the subject must not receive study drug and must not be enrolled in the study. If pregnancy is suspected while the subject is receiving study treatment, the study drug must immediately be withheld until the result of pregnancy testing is known. If pregnancy is confirmed, the study drug will be permanently discontinued and the subject will be followed until the pregnancy comes to term. A Pregnancy Report form will be submitted to the sponsor, initially within 24 hours of the investigator's awareness and at the end of the pregnancy, which includes the outcome of the pregnancy and any complications occurring during the pregnancy or the delivery. If a pregnancy is associated with an SAE, and SAE report form and the pregnancy report form should be submitted to the sponsor within 24 hours of the investigators awareness.

12 Statistics

All statistical processing will be performed using SAS® unless otherwise stated. No interim analyses are planned. Except where noted, all statistical tests will be two-sided and will be performed at the 0.05 level of significance.

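### Five imputations leave avoidable Monte Carlo error in p-values already near 0.05, which can decide where the gated secondary sequence stops

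*Combined protocol and SAP*

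**What the plan says.** Protocol Section 12.8.3 imputes each efficacy variable (IGA, EASI, pruritus severity) within treatment arm. The missing values "will be filled in using the MCMC method 5 times to generate 5 data sets", and the sample code repeats this as nimpute=5. Each completed data set is analyzed, then "CMH statistics will be normalized using the Wilson-Hilferty transformation", and "The results from these analyses will be combined into a single inference using SAS PROC MIANALYZE". On the random seeds the section says: "The 6 random seeds have been prespecified by using a random number generator". All six values are printed, one per arm for each variable.

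The opening of Section 12 says that "all statistical tests will be two-sided and will be performed at the 0.05 level of significance", unless noted otherwise. Section 12.5.2 orders the secondary endpoints and states: "The process will terminate if a nonstatistically significant value is observed". The list holds eight tests (the last two are run together in one bullet): IGA at Week 4, EASI 75 at Weeks 6 and 4, IGA and EASI 75 at Week 10, pruritus at Weeks 2 and 1, and IGA at Week 2.

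The protocol gives no expected missing-data rate, no reason for choosing five imputations and no check of Monte Carlo error. The opening of Section 12 names LOCF as a sensitivity analysis in general terms. The analyses detailed in Section 12.5.5 (LOCF, repeated measures, tipping point) concern Week 6 treatment success, and none is detailed for the gated secondary endpoints.

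**The concern.** A pooled result from five imputations is an average of five random draws. Another seed would give a somewhat different p-value from the same data. That matters little when the p-value is far from 0.05. It matters more when each p-value is a pass-or-stop decision for everything after it.

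The Week 10 endpoints are the natural place to look. They are fourth and fifth of eight. Section 11.1.3 schedules the Week 10 visit only for subjects whose Week 6 visit is not an early-termination visit, so early discontinuers will generally have Week 10 values imputed. A miss at the fourth test blocks the four tests after it. If that miss comes from the draw of imputations and not from the data, endpoints are lost for no scientific reason. A lucky draw can equally open the gate.

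**Working it through.** **1. The plan's own power figure.** Section 12.8.2 assumes success of 23.6% against 6.3% and says that "232 IDP-124 Lotion treated subjects and 116 vehicle lotion treated subjects will have greater than 95% power"; "Nquery Advisor Version 7.0 with the Fisher's exact test option was used to calculate the power".

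- Pooled rate: (232 × 0.236 + 116 × 0.063)/348 = 0.178.
- Null SE: √[0.178 × 0.822 × (1/232 + 1/116)] = 0.0435.
- Alternative SE: √[0.236 × 0.764/232 + 0.063 × 0.937/116] = 0.0359.
- Power: Φ[(0.173 − 1.96 × 0.0435)/0.0359] = Φ(2.445) = 99.3%.

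Exact enumeration of Fisher's test also gives 99.3%. The stated figure is reproduced. The expected primary z is about 0.173/0.0435 = 4.0, well clear of 0.05.

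**2. Formulas for the Monte Carlo error.** For a CMH chi-square X on 1 df, Wilson-Hilferty gives Z = (X^(1/3) − 7/9)/√(2/9), with variance about 1. Rubin's total variance is T = 1 + (1 + 1/m)B, where B is the between-imputation variance. The pooled statistic (mean Z)/√T varies over seeds with SD of about √(B/m)/√T.

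Rough check at 10% missing, where the average fraction of missing information in the simulation was 0.083, so B ≈ 0.083/0.917 = 0.0905. The normal density at the one-sided 5% point (1.645) is 0.103.

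- m = 5: √(0.0905/5)/√1.109 = 0.128; SD of p ≈ 0.128 × 0.103 = 0.013.
- m = 100: √(0.0905/100)/√1.091 = 0.029; SD of p ≈ 0.003.

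This ignores the error in estimating B, so it is somewhat low for m = 5. The simulation gives 0.017.

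**3. Simulation.** From the protocol: 232 and 116 subjects, about 20 centers as strata, within-arm imputation, CMH, Wilson-Hilferty, Rubin pooling, and the 0.05 level. Assumed, because the documents are silent: the missing rate by Week 6, monotone dropout, 15% severe at Baseline, correlation between visits, rounding of imputed IGA, an upper-tail test of the pooled statistic, and a borderline effect of 14.5% against 6.3% (about 60% power). Each of 600 data sets per row received 1,000 imputations, split into sets of 5, 50 and 100. Near 0.05 means a 1,000-imputation p between 0.03 and 0.08; 101 to 112 data sets per row qualified. If a share q of seeds gives significance for one data set, two seeds disagree with probability 2q(1 − q).

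| Missing (assumed) | Disagree, m=5 | m=50 | m=100 | SD of p, m=5 | 5th–95th percentile of p, m=5 | m=100 |
|---|---|---|---|---|---|---|
| 1% | 7% | 2.5% | 2% | 0.004 | 0.047–0.060 | 0.051–0.054 |
| 5% | 23% | 6% | 3% | 0.011 | 0.036–0.071 | 0.046–0.052 |
| 10% | 33% | 9% | 6% | 0.017 | 0.032–0.085 | 0.047–0.056 |
| 20% | 39% | 13% | 8% | 0.026 | 0.026–0.107 | 0.045–0.058 |

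Over all simulated data sets, borderline or not, two five-imputation seeds disagree in 1.3%, 4.1%, 6.4% and 9.0% of trials in the four rows. With 100 imputations this is 0.4%, 0.6%, 1.0% and 1.3%.

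**4. Planned primary effect (23.6% against 6.3%).** With m = 5, two seeds disagree in 0.4%, 0.5% and 1.0% of 1,000 simulated trials at 5%, 10% and 20% missing.

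**5. Stability of these figures.** A separate run at 20% missing, with 55 borderline data sets, gave 41% (m = 5) and 14% (m = 100); its primary-effect counterpart gave 1.6%. At 15% missing, an unrounded cut gave 32% and 6%, and higher success rates (33% against 23%) gave 39% and 11%. Other simulations at 15% missing put about 17% to 20% of five-imputation runs on the minority side. That implies disagreement of up to 2 × 0.17 × 0.83 = 28% to 2 × 0.20 × 0.80 = 32%. The pattern is steady; the second digit is not.

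**The case against.** The plan has good answers to several stronger readings.

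- *The result is not reproducible, or a seed could be chosen after the fact.* The documents do not support this. All six seeds are printed in Section 12.8.3, so given the data and the program there is one p-value and one stopping point.
- *The gate is broken and type I error is inflated.* Not supported. Rubin's rules carry the extra variance through (1 + 1/m)B and the t reference distribution. Nor is the pooled test run on 4 degrees of freedom. With B of 0.08 to 0.14, as seen at 15% missing, the reference df 4 × [1 + 1/(1.2B)]² is about 521 to 193.
- *Any p-value near 0.05 is decided by the seed.* Too broad. The effect depends on a missing rate that the documents do not give. Five of the eight gated tests are at Weeks 1, 2 or 4, where cumulative dropout cannot exceed that at Week 6.
- *The primary result is at risk.* Not at the planned effect, as step 4 shows.

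It is also fair that the 23% to 39% applies only to data sets already borderline. The documents give no effect size for any secondary endpoint, so how often a gate lies near 0.05 is unknown. More imputations cannot remove the noise entirely: for a data set exactly at the threshold, two seeds disagree half the time whatever m is.

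All of this stands. It makes the point one of precision, not validity. It does not explain why the noise should be accepted when it is so cheap to remove.

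**Conclusion.** The point holds as an inexpensive improvement, not as an error in the analysis. For a gated secondary endpoint with a p-value already near 0.05, five imputations leave about a 23% to 39% chance that two equally valid seeds disagree on significance, if 5% to 20% of subjects have missing data by Week 6. One hundred imputations bring this to about 3% to 8% in the main runs (up to 14% in the smaller separate run). Because the sequence stops at the first miss, the noise can decide which later endpoints may be claimed.

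The size rests on assumed missing rates, an assumed weak effect and the simulation choices listed above. It shrinks towards zero as the data approach completeness. The primary conclusion is essentially unaffected at the planned effect.

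**What to change.** Before unblinding, change the number of imputations from 5 to 100 in both places in Section 12.8.3, the step-1 text and the nimpute= option, for IGA, EASI and pruritus. Use the same number in the separate SAP. Keep the six prespecified seeds; alpha, test order and pooling method do not change. Reporting the Monte Carlo error of each gated p-value would be a useful optional addition.

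The cost is a minor protocol change (or a documented departure in the SAP) and slightly more computing time. The choice of 100 is not critical, since 50 already removes most of the disagreement (33% to 9% at 10% missing). Timing matters more: raising the number after a borderline result has been seen would look like a post hoc choice.
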